Recruitment and Informed Consent: The study, including this recruitment plan, will be approved by a Nemours IRB before recruitment begins.. All Nemours health care providers who see T1D patients will receive an e-mail notice describing this study and our plan to contact all potentially eligible parents of Nemours T1D patients about enrollment, All potential Nemours participants that meet enrollment criteria will be identified through Nemours EMR and will receive an emailed study flyer approved by Nemours Marketing and Communications Department,, followed by phone and/or direct contact in the clinic. Online recruitment of the remaining participants will be facilitated by our internet marketing consultant, [name], who will disseminate word of our study and the IRB-approved study flyer using any of several announcements that we have drafted and that have been approved by the Nemours IRB. Internet resources will include Facebook groups such as Diapers and Diabetes and T1D Mod Squad; websites of diabetes organizations such as Children with Diabetes, Children's Diabetes Foundation, and JDRF; and blogs such as Naturally Sweet Sisters. The RCT entails a large group of people using the website together, so we will recruit and enroll all participants over a 1-2 month interval and begin all of them in the trial as close to concurrently as possible. The Nemours IRB has approved our proposal that parental permission and informed consent be obtained electronically since this is adequate participant protection and because it can provide valuable experience to justify this same approach in a future multi-site clinical trial, as we plan.

Study design: The design is a 2X3 randomized treatments design with 2 groups (Website and Usual Care/UC) and 3 measurements (0, 6, and 12 Months). To enable moderation and mediation analyses, randomization will be stratified by site; each site will randomize families to Website and UC in a 2:1 ratio. The primary outcome is change in HbA1c over 6 mos. Usual Care at Nemours is designed to conform to the 2017 ADA *Standards of Medical Care in Diabetes*. All patients will receive the same care offered to patients outside of this study. Those randomized to Website will receive all of the elements of Usual Care, supplemented with access to the online resource for 1 year after randomization.

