Optional Supplemental Methods of Communication with Participating Parents: Participants randomized to Website will also be provided with the option to receive website updates (i.e., new articles posted, active parent-to-parent forum discussions) via an emailed newsletter, Facebook, and/or Twitter. All three of these communication tools will serve the same purpose, which is to encourage participants to visit the website by providing updates through resources that many of them already use frequently (i.e., email and social media). The Facebook group (The New Normal T1D) and Twitter handle (@thenewnormalt1d) will set up as "private" and "protected" such that only select people (i.e., website participants) would be able to access the Facebook

group and see tweets. Users will not be able to post on the Facebook page or tweet to us or each other, thus conversations among users (outside of our website) will not be possible. We are working with the Nemours Social Media Manager to set these up to meet the appropriate privacy specifications. Participants will be required to opt in to receiving the newsletter when they register for the website. Participants will also be to opt in to receiving website updates through Facebook and/or Twitter. If they indicate “yes” then they will be added to the Facebook page and/or encouraged to follow @thenewnormalt1d on Twitter, respectively. Parents randomized to UC will be invited to use the website for 6 months following the first 6 months of the randomization phase of the trial. After the trial is completed, every effort will be made to maintain the website indefinitely.

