Diabetes Self-Management (DMB): The Diabetes Self Management Profile, Self-Report, Parent Form (DSMP-SR)¹⁶³ was derived from the previously validated DSMP structured interview. The 24-item scale quantifies treatment adherence. Mean + SD DSMP total scores (maximum possible = 84) were 54.7 + 12.6 for 145 parents. Internal consistency was α =0.80 and correlation with HbA1c was r =0.46.

Glycated Hemoglobin (HbA1c): For parents of children who receive T1D care at a Nemours facility, the child's most recent HbA1c, an index of average glycemia over the prior 2-3 months, will be obtained from the electronic medical record for the prior 12 months and for each T1D encounter occurring during the child's study enrollment. For participants enrolling online from non-Nemours centers, glycemic control will be measured via HbA1c collected using HemaSpot SE Blood Spot Collection Devices (dried blood spots [DBS]) obtained at 0, 6 and 12 months and analyzed at CoreMedica Laboratories in [name]'s Summit, MO. Correlations between DBS and standardized venous HbA1c are high and sensitivity and specificity for DBS for HbA1c are excellent^{165,166}. Higher values indicate higher average blood glucose over the prior 2-3 months.

Measures obtained at 6 months and 12 months only:

Website utilization: For each website user, we will track time-stamped logins and logouts, duration of login periods, hits on and duration of activity within specific website elements, etc. to provide careful tracking of extent and type of website use by each registered parent.

Qualitative interview: Parents will complete a qualitative interview at 3 months, 6 months and post-RCT, or earlier if the parent withdraws. The interview will obtain parents' perspectives of the website, suggested changes to content and design, advantages and disadvantages, reasons for low utilization, etc. We expect that this interview will yield relatively brief and focused responses from parents. Trained content analysts will employ a descriptive level of analysis, using a well-accepted method of content analysis via HyperRESEARCH software to extract the primary themes that emerge during these interviews. Analysts will be trained to a criterion of 90% inter-rater reliability. [name] will direct incorporation of these themes into the website.

Table 1. Measurement schedule for the randomized controlled trial phase of the proposed work.

Measure	Baseline	6 Months	12 Months
Demographic Information	•		
HbA1C	•	•	•

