H1: Compared to UC participants, Website participants will have significantly more favorable status at 6 and 12 months on HbA1c (primary outcome) and secondary outcomes consisting of change in questionnaire scores at follow-up visits.

H2: Website treatment effects will be moderated by parental socioeconomic status and questionnaire scores at baseline visits

H3: Website treatment effects will be mediated by changes in change in questionnaire scores at follow-up visits.

H4: Among Website participants, the above treatment effects will be mediated by Website utilization (More utilization predictive of more beneficial effects).

Perhaps more importantly, this feasibility trial will yield rich data that will be used for estimation of effect sizes and sample size requirements for a future multi-center trial,¹⁷⁹⁻¹⁸⁰ and will enhance that application by:

1. Estimating Website-UC effect sizes (Cohen's *d* index)¹⁷⁹⁻¹⁸¹ at 6 and 12 months on the primary and secondary outcome variables.
2. Exploring utilization of the online resource, by examining demographic variables and individual characteristics of parents and children as moderators of Website use, and change in time-varying variables as mediators of change in Website use over 6 and 12 mo.¹⁷³⁻¹⁷⁸
3. Use of Structural Equation Modeling to evaluate and refine the conceptual model put forth earlier.¹⁸¹
4. Analyzing Mid-RCT and Post-RCT qualitative interviews of participants will provide additional information to drive refinements in the WEBSITE for future trials that could enhance WEBSITE use and benefit.

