Informed Consent Process: Using IRB-approved, electronic informed consent infrastructure established in ongoing research at Nemours by [name] (1-R01HL114899-01: Use of Mobile Devices and the Internet to Streamline an Asthma Clinical Trial), parents will electronically authenticate an IRB-approved informed consent form that will include all of the federally required elements of informed consent and that fulfills Nemours pertinent policies and procedures. Per Nemours policy, assent is not required for children under 7 years of age to participate in research if appropriate parental permission has been obtained, as it will be in this case.

Sources of research data This study will involve parental completion of questionnaires at baseline, 6 and 12 months and either 1. For parents of Nemours patients, access to the child's electronic health record for retrieval of recent HbA1c results and documentation of symptomatic and severe hypoglycemic episodes or 2.).

For parents recruited online, parents will collect and submit dried blood spots. Parents' use of the online resource will also be tracked automatically. At 3, 6 and 12 months after randomization or upon withdrawing the study, parents randomized to Website Access will be asked to complete a qualitative interview about their experiences with use of the website and their suggested refinements.

Potential risks: The most likely risks are privacy threats and possible loss of confidentiality, but it would be difficult to characterize the potential for harm to participants since the questions do not address illegal, unethical or stigmatizing behaviors and all of the participants are adults who may simply decline to answer any question that is perceived to be threatening. Participants randomized to UC may be at somewhat higher risk of deterioration in metabolic, behavioral and affective outcomes than those randomized to SMP. There is little reason to believe that parent or child participants will fare more poorly due to study involvement than if they had not enrolled.

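### Usual Care access to the website opens by elapsed time and is not tied to the family's own 6-month assessment, so some month-6 values may be taken after exposure

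*Combined protocol and SAP*

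**What the plan says.** The UC access rule is in section 4.2, under Optional Supplemental Methods of Communication with Participating Parents: "Parents randomized to UC will be invited to use the website for 6 months following the first 6 months of the randomization phase". Website families have access for the full year after randomization (Study design).

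The endpoint is fixed under Study design: "The primary outcome is change in HbA1c over 6 mos". Hypothesis H1 (Primary Analyses) covers both follow-up times: "Website participants will have significantly more favorable status at 6 and 12 months on HbA1c (primary outcome").

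HbA1c is collected in two ways (Glycated Hemoglobin paragraph). For Nemours children the latest result "will be obtained from the electronic medical record for the prior 12 months and for each T1D encounter occurring during the child's study enrollment". For children recruited online, parents collect dried blood spots "obtained at 0, 6 and 12 months and analyzed at CoreMedica Laboratories". The same paragraph describes HbA1c as "an index of average glycemia over the prior 2-3 months". On questionnaires, the Human Subjects section (Sources of research data) says: "This study will involve parental completion of questionnaires at baseline, 6 and 12 months". They are completed online.

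Four things are not stated:
- a month-6 window for any of these measures;
- which Nemours encounter supplies the month-6 HbA1c;
- whether the 6 months run from each family's randomization or from one date for the whole trial;
- what happens to a UC value obtained after access opens. The Full Analysis Set (Fundamentals) takes any parent with 6- or 12-month data.

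**The concern.** Months 0 to 6 are the only period in which Website is compared with a UC group that has not been offered the website. The 6-month HbA1c change is the primary outcome, and Cohen's d at 6 months is one of the quantities the trial is meant to hand to a future trial.

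The access date and the assessment date are set by different mechanisms. The first is elapsed time. The second depends on clinic scheduling for Nemours children, and on when a parent returns a card or completes a form for the home-collected measures. Where the assessment falls after the access date, a UC family may already be using the intervention when its month-6 value is obtained. A Website family measured equally late stays in its assigned condition. If the website helps, the UC mean then moves toward the Website mean, and both the contrast and d are understated. HbA1c is partly protected because it averages 2 to 3 months. Questionnaires have no such averaging.

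**Working it through.** The documents give no power, target effect, standard deviation or visit window, so there is no planned figure to reproduce. What follows shows how far the answer depends on choices the plan leaves open.

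**Inputs from the documents.** HbA1c averaging window 2 to 3 months. Up to 120 Nemours enrollees (4.2, Participants). About 225 children projected (Inclusion of Children). 150 families at 2:1, so about 100 Website and 50 UC (RCT Analytic Plans). Enrollment over 1 to 2 months (Recruitment and Informed Consent). Two-sided alpha 0.05.

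**Assumptions not in the documents.** Nemours visits every 3 to 6 months with uniform offsets, even weighting of the HbA1c window, every UC parent takes up access at once, an immediate full effect, and a Website effect already level by month 6. The exposed share of the UC window, f, then equals the proportional loss in the contrast.

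**1. Nearest-encounter rule, per-family clock.** The encounter nearest month 6 lies within half a visit interval on either side, so 50% fall after it.
- 3-month spacing: the delay in the late half is uniform on 0 to 1.5 months, mean 0.75. Exposed share 0.75/3 = 25% to 0.75/2 = 37.5%.
- 6-month spacing: the delay is uniform on 0 to 3 months, mean 1.5. Exposed share 1.5/3 = 50% with a 3-month window. With a 2-month window it is (2/3)(1/2) + (1/3)(1) = 67%.
- Over all Nemours UC: half of these, 12.5% to 33%.
- Over all UC: times 120/225 = 0.533, giving 6.7% to 17.8%. With 120 of 150 (0.8) it would be 10% to 26.7%.

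**2. Other selection rules, same assumptions.**
- Last HbA1c before month 6: f = 0 for Nemours children.
- First encounter after month 6: the delay is uniform over the whole interval. The exposed share of Nemours UC is 50% (3-month spacing, 3-month window) to 83% (6-month spacing, 2-month window). Times 0.533, this is 27% to 44% of all UC.

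**3. Trial-wide clock.** Suppose access opens for everyone 6 months after the first enrollment, and enrollment is even over e months. A UC family assessed exactly on time then has on average e/2 months of access.
- e = 1: f = 0.5/3 to 0.5/2 = 17% to 25%.
- e = 2: f = 1/3 to 1/2 = 33% to 50%.

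A clock started at the last enrollment would give none of this.

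**4. Generic lateness, any HbA1c source.** f = (share late) × (weeks late / window), with a window of 8.7 to 13 weeks.

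| UC assessed late | Effect retained | Power if 80% without dilution |
|---|---|---|
| 10%, by 2 weeks | 98% | 78–79% |
| 25%, by 4 weeks | 88–92% | 70–73% |
| 50%, by 8 weeks | 54–69% | 33–49% |

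Power is Φ(2.80(1 − f) − 1.96). The 80% benchmark corresponds to d = 2.80 × √(1/50 + 1/100) = 0.485 at 100:50, or 2.80 × √(1/75 + 1/150) = 0.396 at 150:75. On the same formula, the 6.7% to 17.8% of step 1 would take 80% power to about 74% and 63%.

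Step 1 leaves out late dried-spot cards, and none of the steps covers questionnaires.

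**The case against.** The strongest reply is that the plan can be read without any fault. Measurement is at 6 months, the invitation follows the first 6 months, and assessing first and inviting second fits both sentences. That is right: a reader might infer that the protocol puts access before assessment, and it does not. UC parents are also only invited, so exposure needs uptake as well as a late measurement or a trial-wide clock. What survives is that nothing enforces the benign order.

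A reader might also infer that about half of Nemours UC children will have a post-access value. That follows only from a nearest-encounter rule, which the documents do not contain. The HbA1c paragraph speaks of the child's latest result. Applied at month 6 on a per-family clock, that would be a look-back, and the Nemours exposure would vanish. But the same sentence also collects values "for each T1D encounter occurring during the" child's enrollment and does not say which one serves as month 6, so the look-back reading is not secured either.

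Nor is 7% to 18% an upper bound. Late dried-spot samples add to it, and other selection rules exceed it. In the other direction, saying that lateness affects only UC is too strong: if the Website effect is still growing at month 6, a late Website value has gained exposure too, which partly offsets the dilution.

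It is fair, finally, that with few and short delays the HbA1c loss is small, and that this is a preliminary trial with several aims besides d.

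**Conclusion.** The concern holds as a gap in the plan. UC access is time-triggered, month-6 measurement is unwindowed, and nothing connects the two or governs UC values taken after access. Followed as written, the plan allows some UC primary-endpoint values and questionnaires to be obtained after website use. If the website helps, the 6-month contrast and d would tend to be understated.

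The size is not determinable from the documents. About 7% to 18% of the HbA1c window over all UC is an illustration resting on the nearest-encounter rule, 3- to 6-month visits, 120 of 225 children from Nemours, full uptake and an immediate effect. The other rules give anything from near zero to substantially more. The effect on questionnaires is unquantified.

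The correction is worth making because it is cheap, and because an unexposed 6-month value cannot be recovered once a UC family has used the site. The 12-month contrast, where UC families may have had up to 6 months of access, is a separate matter.

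**What to change.** 1. In section 4.2 (Optional Supplemental Methods of Communication), run the 6 months from each family's own randomization. Open a UC family's access when its 6-month questionnaires and HbA1c are in, or when a pre-set month-6 window closes, whichever comes first.
2. In the measures and analysis sections, define that month-6 window and the rule for choosing the HbA1c value, and apply both identically to the two arms.
3. Add a sensitivity analysis that excludes UC month-6 values taken after the family's first login. The time-stamped logins are already tracked.

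The exclusion in step 3 should not be the primary analysis. Dropping post-login values in UC alone would make UC measurements systematically earlier than Website ones and would select on behaviour after randomization.

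The cost is a registration rule and a few sentences of protocol and analysis text, with no extra patients or visits. Some UC families would get access somewhat later, so their 6 months of use may be shortened or run past month 12, and the protocol should say which. A family whose data arrive only after the window closes may still be exposed. Steps 2 and 3 deal with that remainder.

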Having designed, built, tested, validated and refined the proposed online resource, we will be well-positioned to plan and complete a rigorous randomized controlled trial to evaluate effects of portal use/access on metabolic, behavioral, affective and social outcomes of T1D care for YC-T1D. While completing Aim 3, we will solidify partnerships with several key organizations (PEDSnet, T1D Exchange, JDRF, American Diabetes Association) to enable economical completion of a major multisite trial. The design of the proposed preliminary RCT will

position us to propose a completely electronic multisite RCT that does not require face to face contact between parents and the research team and can be completed totally in cyberspace.

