Participants: The RCT will enroll up to 300 parents of children <6 years old who receive T1D care at any of five Nemours Children's Health System sites in the Delaware Valley and Florida or who are recruited online

using a variety of internet resources from among eligible parents who live elsewhere in the United States. . As noted in Facilities and Resources, Nemours YC-T1D population was recently estimated at 213 patients, with a slightly increasing trend over the past 4 years. We anticipate that about 25% will be ineligible for one or more reasons and that another 10-15% will not be interested in participating in the study. With a 60% recruitment rate, we project that parents of up to 120 Nemours patients will enroll and that we will recruit the remaining parents via the various online methods, all of which are established, publicly available resources of the Diabetes Online Community that are already frequented by parents of this clinical population. Since parents will collect and ship dried blood spot samples from children who do not receive T1D care at Nemours, study participants must reside in the United States due to logistic and cost considerations associated with international shipping of these samples. One parent's participation is required, but two parents of the same child will be encouraged to take part, in which case the mother and father will complete the measures separately. We estimate that 75 fathers will enroll, but we will enroll any/all who wish to do so. Minorities and those with economic or educational disadvantages may have limited access to social media. If necessary to achieve sample composition consisting at least of 28% racial minorities and of 7% Hispanic ethnicity, we will continue selective recruitment of racial and ethnic minorities after concluding recruitment of non-Hispanic Whites in order to oversample from these groups to ensure that our parent sample is very diverse. There is no minimum duration of T1D, nor is there an HbA1c cutoff as the website is intended for all YC-T1D parents.

Inclusion criteria: Parent or legal guardian of a child with physician diagnosis of T1D; Parent age ≥ 18 years; Child with T1D is currently < 6 years old; Parent able to read and comprehend English; Regular access to the internet.

Exclusion criteria: Inability to read/comprehend study questionnaires and decision aids in English; Participating parent or the child with T1D lives outside of the United States.

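### HbA1c is read by two different routes, but its effect size is planned without a split by route, so the figure may not carry over to a future trial with a different mix

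*Combined protocol and SAP*

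**What the plan says.** **Two routes.** Under Glycated Hemoglobin in section 4.2, values for Nemours patients "will be obtained from the electronic medical record for the prior 12 months and for each T1D encounter occurring during the child's study enrollment". Children enrolled online are measured with "HemaSpot SE Blood Spot Collection Devices (dried blood spots [DBS]) obtained at 0, 6 and 12 months", read at one named laboratory. The Participants paragraph adds that "parents will collect and ship dried blood spot samples from children who do not receive T1D care at Nemours".

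**Comparability.** The only statement is "Correlations between DBS and standardized venous HbA1c are high and sensitivity and specificity for DBS for HbA1c are excellent". No bias, limits of agreement, error SD or calibration is given, and no paired clinic and dried-spot samples are planned.

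**Endpoint and model.** The Study design paragraph says "The primary outcome is change in HbA1c over 6 mos"; hypothesis H1 words it as status at 6 and 12 months. The Primary Analyses paragraph names a linear mixed model. HbA1c source does not appear among its terms, the candidate moderators or the sensitivity analyses.

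**Use of the result.** RCT Analytic Plans puts its emphasis on effect sizes for powering later trials. Item 1 of the list after the hypotheses is Cohen's d "at 6 and 12 months on the primary and secondary outcome variables", with no split by source and no definition of the SD that d divides by. Section 2 says the present trial will "position us to propose a completely electronic multisite RCT that does not require face to face contact between parents and the research team".

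**Stratification.** Section 4.2 stratifies randomisation by site. The Human Subjects section stratifies by insulin modality and recruitment method (Nemours or online).

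**The concern.** Two methods can correlate highly and still differ in level or in random error. Sensitivity and specificity describe classification at a cut-off, whereas this endpoint is continuous. So the cited evidence does not show that the two routes give the same SD of change.

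Cohen's d is a mean difference divided by an SD. If the SD differs by route, a d computed across both depends on this trial's particular mix and carries over only to a trial with a similar mix. Planning figures for the next trial are a main stated product here. A planner given one undivided d cannot re-weight it to the method the next trial will use. Unlike sampling error, this mismatch does not show in the confidence interval and does not shrink with a larger sample.

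**Working it through.** **The plan's own figure.** RCT Analytic Plans says 150 families, randomised 2:1, will suffice. It states no effect, SD, power or precision target, so the 150 cannot be reproduced.

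**Dried-spot share, w.** Section 4.2 projects at most 120 Nemours children. The documents give three totals:
- 150 families (RCT Analytic Plans): (150 − 120)/150 = 30/150 = 20%
- 225 children (Inclusion of Children): 105/225 = 47%
- 300 families, the upper limit in Human Subjects: 180/300 = 60%

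The section 4.2 rates can also be read as 213 × 0.75 × 0.60 ≈ 96 Nemours children. The shares would then be 36%, 57% and 68%, and the shortfall at each total smaller. The Inclusion of Children paragraph mentions only medical-record data for its 225 children, so the 105 is a remainder, not a stated number.

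**Extra dried-spot variance, λ.** This is the added outcome variance with dried spots as a fraction of the clinic variance. The documents give no value, so 0.10 to 0.50 is an assumption. An error SD of e per reading adds 2e² to the variance of a change. With an assumed clinic SD of change of 0.8 percentage points, e = 0.8 × √(λ/2), which is 0.18 to 0.40.

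**Formulas** (same raw effect in both sources; two-sided 0.05, 80% power):
- Pooled d = d_clinic/√(1 + wλ)
- Dried-spot-only d = d_clinic/√(1 + λ)
- Required-size ratio R = (1 + λ)/(1 + wλ)
- Actual power of a dried-spot-only trial sized on the pooled d = Φ(2.80/√R − 1.96)

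Example with λ = 0.20, w = 0.20: R = 1.20/1.04 = 1.154. Power = Φ(2.80/1.074 − 1.96) = Φ(0.65) = 74%. With an assumed d_clinic of 0.30, the pooled d is 0.294 (182 per arm) and the dried-spot-only d is 0.274 (210 per arm).

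| λ | w = 20% | w = 47% | w = 60% |
|---|---|---|---|
| 0 | R 1.00, power 80% | R 1.00, power 80% | R 1.00, power 80% |
| 0.10 | R 1.08, power 77% | R 1.05, power 78% | R 1.04, power 79% |
| 0.20 | R 1.15, power 74% | R 1.10, power 76% | R 1.07, power 77% |
| 0.50 | R 1.36, power 67% | R 1.22, power 72% | R 1.15, power 74% |

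**Reverse case.** If clinic values carry the extra variance, as a fraction κ of the dried-spot variance, a dried-spot-only trial needs 1/(1 + (1 − w)κ) of the size planned. For κ = 0.20 and w = 0.20 this is 1/1.16 = 0.86, so the trial is oversized.

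**Precision of by-source estimates.** The 95% half-width of d is about 1.96 × √(1/n_UC + 1/n_Web), with 2:1 allocation and no dropout:
- 30 dried-spot children (10 and 20): 1.96 × √0.15 = 0.76
- 105 (35 and 70): 0.41
- 180 (60 and 120): 0.31
- Whole trial of 150 (50 and 100): 1.96 × √0.03 = 0.34

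**The case against.** The strongest reply is that nothing shows the next trial will use dried spots only. The Human Subjects section describes the present trial, with both routes, as needing no face-to-face contact and as repeatable on a larger scale. Record retrieval therefore already fits an electronic trial, and if the next trial keeps a similar mix, the mixed-source SD is the right one. This stands. A reader might infer that the planning figure will not fit the next trial, or that the next trial will be undersized; the documents support neither.

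The direction is also open. Dried spots are read at one laboratory at set times, while clinic values follow encounters across five sites. Clinic changes could be the noisier ones.

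A reader might further infer that mixing sources biases the treatment comparison. That does not follow. Stratifying by recruitment method, as in Human Subjects, would balance source between arms. Nor does a constant level offset matter for the primary endpoint, because it cancels in within-child change. The plan also does not say that correlation justifies pooling: the sentence describes the assay, and pooling is inferred from the absence of any split.

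Finally, the correction is small beside sampling error. In the example it moves d by 0.02, against a half-width of 0.34 at 150 families. The SD ratios, √R, run from 1.02 to 1.17, while the 95% interval for an SD is about −20% to +34% with 30 children and −12% to +16% with 105. This rules out a firm instruction to size the next trial on the dried-spot SD alone. It does not remove the case for reporting by source: by-source figures can be re-weighted to whatever method is chosen later, and a single d cannot. They could be extracted afterwards from the same data, but pre-specifying them costs almost nothing.

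**Conclusion.** The point holds in a limited form. HbA1c comes from two routes whose equality of level and error is not shown, and the planned d has neither a split by source nor a defined SD. It may not carry over to a trial with a different mix, and the plan gives no way to tell.

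Under the assumed 10% to 50% extra dried-spot variance, and shares of 20% to 60%, a dried-spot-only trial sized for 80% power would have about 67% to 79% and would need 4% to 36% more participants. The effect is zero if the variances are equal and reverses if clinic values are noisier. The size rests wholly on that assumed variance, on an equal raw effect in both sources, and on a future trial that changes the mix. It is a planning and reporting weakness, worth correcting because planning figures are a main product of this trial.

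**What to change.** 1. **Effect sizes (RCT Analytic Plans, item 1):** keep the pooled estimate. Add the HbA1c mean difference in percentage points, the SD and d for each source, with confidence intervals. Define the SD used to standardise.
2. **HbA1c mixed model (Primary Analyses):** include source, which corresponds to the recruitment-method stratum in Human Subjects, and let the residual variance differ by source.
3. **Future sample size:** state that it will use the SD matching that trial's own HbA1c method, allowing for the uncertainty in that SD.
4. **Glycated Hemoglobin paragraph:** state that the two methods are not assumed interchangeable.
5. **Stratification:** reconcile section 4.2 (by site) with Human Subjects (by insulin modality and recruitment method).

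**Cost:** wording and one model option, with no new data. The downside is imprecision: about ±0.76 on d with 30 dried-spot children and ±0.41 with 105. Source is also confounded with population (Nemours or online), and no paired samples are planned, so by-source results cannot isolate assay error and should not be presented as doing so.
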